### 5. Endpoints

#### *Primary Safety Endpoint*

The primary safety endpoint is defined as the proportion of subjects experiencing a MAE within 30 days post-implantation. MAEs include the occurrence of any of the following events:

- All-cause mortality
- Bowel ischemia
- Myocardial infarction
- Paraplegia
- Procedural blood loss  $\geq 1000$  cc
- Renal failure
- Respiratory failure
- Stroke

#### *Primary Effectiveness Endpoint*

The primary effectiveness endpoint is defined as the proportion of subjects with both technical success at the time of index procedure and treatment success at 12 months post-implantation. Successful aneurysm treatment is achieved based on the following criteria:

- Technical success at the index procedure (as assessed intra-operatively) is defined as successful delivery and deployment of the Endurant Evo AAA Stent graft system in the planned location and with no unintentional coverage of both internal iliac arteries or any visceral aortic branches and with successful removal of the delivery system

AND

- Treatment success consisting of freedom from:
  - AAA diameter increase, defined as  $> 5$  mm increase in maximum diameter as measured on CT scan (or MRA/MRI) at 12-month follow-up as compared to 1-month imaging
  - Types I and III endoleaks at 12-month follow-up including those requiring intervention through 12 months
  - Aneurysm rupture within 365 days
  - Conversion to surgery within 365 days
  - Stent graft migration resulting in a serious adverse event or requiring secondary intervention through 12 months

- o Stent graft occlusion through 12 months

#### *Secondary Endpoints*

The following secondary endpoints will be evaluated:

- All-cause mortality within 30, 183, and 365 days
- Aneurysm-related mortality within 30, 183, and 365 days
- Secondary procedures to correct Type I and III endoleaks within 183 and 365 days
- Secondary procedures within 183 and 365 days
- Serious adverse events within 30, 183, and 365 days
- Conversion to open surgery within 183 and 365 days
- Aneurysm ruptures within 183 and 365 days
- Major adverse events within 183 and 365 days
- Stent graft migration at 6- and 12-month follow-up visits (as compared to 1-month imaging)
- Aneurysm expansion >5 mm at 6- and 12-month follow-up visits (as compared to 1-month imaging)
- All endoleaks based on imaging findings at 1-, 6-, and 12-month follow-up visits
- Stent graft occlusions based on imaging findings through 1-, 6- and 12 months
- Device deficiencies based on imaging findings through 6 and 12 months.

#### *Additional Observations*

The following acute procedural observations and clinical utility measures will be reported:

- Mean duration (min) of procedure (time between initial skin access to final skin closure)
- Proportion of subjects who underwent general/local/epidural/spinal anesthesia
- Proportion of subjects who underwent unilateral/bilateral percutaneous access
- Proportion of subjects requiring blood transfusions, excluding cell saver
- Mean volume (cc) of estimated blood loss
- Mean duration (min) of radiation exposure
- Radiation exposure (mGy)
- Mean length of time (hours) in intensive care unit
- Mean length of time (days) of hospital stay (from the index procedure to hospital discharge)

Health-related quality of life outcomes will be assessed at baseline, 1-month, 6-month and 12-month follow-up visits using the EQ5D questionnaire

## **6. Definitions**

Detailed definitions for the primary and secondary endpoints are provided in Clinical Investigational Plan Appendix L.2.

## **7. Interim Analysis**

No interim analysis is planned prior to the PMA submission.

## **8. Statistical Methods of Analyses**

### **8.1. General consideration**

All observations will be analyzed descriptively. In general, qualitative parameters will be described by their distribution frequencies; quantitative parameters will be described by their

mean, standard deviation, minimum, maximum, median, and number of subjects with assessable data.

For events such as AEs, deaths and secondary procedures, that can occur or are observed at any time during the study, no time window will be applied. For such events, an event that occurs “within 1 month or 30 days” is an event that takes place between Days 0 to 30, inclusive. Similarly, an event that occurs “within 12 months or 365 days” is an event occurring between Day 0 to Day 365, inclusive. Date of event onset will be used to determine when the event occurred. Day 0 is referring to the day of index procedure.

For image-based assessments, such as stent-graft endoleak, patency, and other observations, the following time windows will be applied for by-visit data summaries:

**Table 2: Time Windows for Statistical Analyses**

Study Visit	Target Day	Time Window
Implant	Day 0	Day 0
1 Month	Day 30	1 – 90 days
6 Months	Day 183	91 – 304 days
12 Months	Day 365	305 – 548 days
In case long term follow up data will be collected, the following time windows will apply.		
2 Year	Day 731	549 – 913 days
3 Year	Day 1096	914 – 1278 days
4 Year	Day 1461	1279 – 1644 days
5 Year	Day 1826	1645 – 2009 days

If different type of images are used but have different finding in the same time window, the imaging technique and sensitivity matrix (Appendix 12.1) will be applied. Finding from higher visibility image will be used for analysis. If there are two or more assessments from the same type of image in the same time window, then the assessment closest to the target day will be used in the analysis of event rate at a given time point.

Statistical analyses for this study will be performed using the Statistical Analysis System (SAS) for Windows (Version 9.1 or higher) or other widely-accepted statistical or graphical software.

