**Table F-1: Post-Implantation Follow-Up Schedule and Windows**

Follow-Up Visit	Window Start Day	Target Day	Window Close Day
1 Month ( $\pm$ 15 days)	15	30	45
6 Month ( $\pm$ 30 days)	153	183	213
12 Months (-30/+56 days)	335	365	421
24 Months ( $\pm$ 56 days)	675	731	787
36 Months ( $\pm$ 56 days)	1040	1096	1152
48 Months ( $\pm$ 56 days)	1405	1461	1517
60 Months ( $\pm$ 56 days)	1770	1826	1882

At all required follow-up visits subjects will undergo the following assessments:

- Physical Exam (to be reported in FUP eCRF until 24 months only)
- CT/MR with contrast and non-contrast (2 cm above the origin of the celiac artery through the bifurcation of the femoral arteries)
- Abdominal X-ray (4-view, KUB)
- EQ5D questionnaire (until 12 months F/U only)
- Adverse event assessment
- Concomitant Medication (to be reported in FUP eCRF until 24 months only)

If a CT/MR is acquired at discharge (or before Day 15) due to medical necessity, or at the discretion of the investigator, it may be used to meet the 1-month follow-up visit CT/MR requirement and, acquisition of an additional 1-month CT/MR with contrast would not be required.

Abdominal X-rays should be completed via a four-view kidney, ureter, bladder (KUB) X-ray. Posterior/anterior (PA) and lateral images are recommended for visualization of the stent graft. Ensure the entire device is captured on images for assessment.

If conversion to open repair is required during the follow-up period, then the subject will be followed for 30 days after the conversion, at which time the subject will be exited from the study. Please refer to Device Explant and Returned Product Instructions, located in L.4 of the protocol.

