Stent Graft Wireform Fracture	Fracture or breakage in stent graft wireform.
Stent Graft Wire Detachment From Fabric	Detachment of the Stent Graft Wire from the fabric.
Suprarenal Bare Stent Detachment from Fabric	Detachment of the Suprarenal Bare Stent from the fabric.
Stent Graft Dilatation	Graft dilatation >50% of the manufacturer's labeled diameter as determined by CT scan, angiography, and/or direct observation at surgery or autopsy.
Stent Graft Extrusion or Erosion	Extrusion or erosion of the metal frame through the full thickness of the vessel wall as determined by CT, angiography, and/or direct observation at surgery or autopsy.
Stent Graft Twisting	Stent Graft obstruction in the vertical plane as determined by CT scan or angiography resulting in an unintentional obstruction (>50%) of blood flow through the vascular lumen and not caused by anatomy of the vessel wall.
Stent Graft Kinking	Stent Graft obstruction in the horizontal plane as determined by CT scan or angiography resulting in an unintentional obstruction (>50%) of blood flow through the vascular lumen and not caused by anatomy of the vessel wall.
Access Failure	Inability to insert device due to mechanical failure or anatomic exclusions of the femoral or iliac arteries.
Deployment Failure	Deployment failure due to subject anatomy or mechanical failure. This specifically refers to deployment of the stent graft from the delivery system.

Additional Definitions	Definition
Stent Graft Stenosis	Hemodynamically significant (>50%) reduction in the diameter of the stent graft lumen as compared to the reference diameter and not caused by anatomy of the vessel wall.
Stent Graft Infection	The development of a perigraft infection confirmed by direct examination, CT, and/or perigraft aspiration.
Technical Success	Successful delivery and deployment of the stent graft (assessed intra-operatively) in the planned location and with no unintentional coverage of internal iliac arteries or any visceral aortic branches and with the removal of the delivery system.

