## 12. Appendices

### 12.1. Imaging Technique and Sensitivity

Anatomy/Stent Graft Issue Detected	CT with contrast	CT without contrast	MRA	MRI	Abdominal X-ray	Duplex CDUS (Ultrasound)	Angiogram, Aortogram and Arteriogram
AAA Diameter and Length	1	2	1	2	4	3	3
Stent graft migration	1	2	1	2	3	4	2-3
Stent graft fracture	2	3	2	3	1	4	2-3
Stent graft kinking	2	3	2	3	1	4	2-3
Stent graft twisting	2	3	2	3	1	4	2-3
Stent graft patency	1	4	1	4	4	2	2-3
Endoleaks	1	4	1	4	4	2	2-3
Occlusion	1	4	1	4	4	2	2-3
Stenosis	1	4	1	4	4	2-3	2-3
Stent Graft Fabric Defect	1	4	1	4	4	4	2-3
1 = Highly visible		2 = visible		3 = Not very visible (potential artifacts)		4 = Invisible	

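### For stent graft kinking and twisting, the SAP's image ranking puts plain X-ray above CT and angiography, the only methods named in the protocol's definition

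*SAP*

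**What the plan says.** SAP 8.1, in the text under Table 2, gives the rule for conflicting images. It applies "If different type of images are used but have different finding in the same time window" and sends the analyst to the matrix in Appendix 12.1, with the outcome: "Finding from higher visibility image will be used for analysis". No item is exempted.

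The matrix columns run contrast CT, non-contrast CT, MRA, MRI, abdominal X-ray, duplex, angiogram; 1 is the best visibility and 4 means invisible. The rows at issue are "Stent graft kinking 2 3 2 3 1 4 2-3" and "Stent graft twisting 2 3 2 3 1 4 2-3".

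SAP section 6 takes its endpoint definitions from protocol Appendix L.2. There kinking is "Stent Graft obstruction in the horizontal plane as determined by CT scan or angiography resulting in an unintentional obstruction (>50%) of blood flow" through the lumen. Twisting has the same wording except that it refers to the vertical plane. X-ray is not named in either.

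Both items are listed in L.2 as device deficiencies. Device deficiencies on imaging through 6 and 12 months are a secondary endpoint (SAP section 5), computed by Table 4 (SAP 8.5). Protocol F.2.3 requires both CT/MR and a four-view abdominal X-ray at every follow-up visit.

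The protocol prints the same matrix in L.6 but does not rank findings by it. Protocol H.1 takes the assessment nearest the target day. The ranking rule is in the SAP only.

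**The concern.** A visibility rank and an endpoint definition answer different questions. X-ray may show the shape of a stent frame best, but L.2 makes kinking or twisting an event only if flow is obstructed by more than half, and it says which imaging methods establish that. The SAP rule lets a method outside the definition decide the outcome over methods inside it.

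The error can go either way. A kink or twist that meets L.2 on CT may be scored absent in that window because the X-ray was read as negative. An X-ray appearance without the required obstruction on CT may be scored present. Because CT and X-ray are both scheduled at each visit, the conditions for a conflict exist in every window. Graft flexibility, limb design and conformability are stated design targets of the device (protocol B.1), so these two items bear on what the trial set out to describe.

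**Working it through.** No sample size, power or event figure enters this point. The check applies the SAP 8.1 rule (lowest rating number wins) to the Appendix 12.1 matrix and compares the winning modality with the L.2 definition.

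| Matrix row | Contrast CT | Non-contrast CT | X-ray | Angiogram | Prevails, X-ray v. contrast CT | L.2 definition |
|---|---|---|---|---|---|---|
| Kinking | 2 | 3 | 1 | 2-3 | X-ray | CT or angiography, >50% flow obstruction |
| Twisting | 2 | 3 | 1 | 2-3 | X-ray | CT or angiography, >50% flow obstruction |
| Fracture | 2 | 3 | 1 | 2-3 | X-ray | No modality named |
| Patency | 1 | 4 | 4 | 2-3 | CT | (no separate definition) |
| Occlusion | 1 | 4 | 4 | 2-3 | CT | Several modalities accepted |
| Stenosis | 1 | 4 | 4 | 2-3 | CT | >50% lumen reduction |
| AAA diameter | 1 | 2 | 4 | 3 | CT | n/a here |
| Migration | 1 | 2 | 3 | 2-3 | CT | n/a here |
| Endoleaks | 1 | 4 | 4 | 2-3 | CT | n/a here |

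1. X-ray ranks first in three of the ten matrix rows: fracture, kinking and twisting. (The tenth, fabric defect, also has contrast CT at 1 and X-ray at 4.)
2. Of those three, fracture raises no conflict, because its L.2 definitions name no modality. Kinking and twisting do, because L.2 names the methods and adds a flow threshold.
3. The matrix has no row for flow obstruction. The nearest rows are patency ("Stent graft patency 1 4 1 4 4 2 2-3"), occlusion and stenosis. All three rate X-ray 4, and L.2 defines stenosis by a lumen reduction above 50%. The implication is that X-ray cannot establish the threshold L.2 requires.
4. The imaging components of the primary effectiveness endpoint are diameter increase, Type I and III endoleak, migration and occlusion. Contrast CT is rated 1 in each of those rows and X-ray 3 or 4, so this problem does not reach them. The primary safety endpoint does not use these images.

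**The case against.** **The protocol governs.** SAP section 1 makes the protocol the primary resource where clarification is needed. If L.2 is applied first, an X-ray appearance without the CT or angiographic criterion is never an event. This softens the conflict, but the 8.1 rule is explicit and a programmer would follow it as written.

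**The matrix rates X-ray 1 for kinking and twisting.** True, and a reader might infer from the other rows that the SAP itself declares X-ray unable to show the obstruction. It does not. That is an inference from the patency, occlusion and stenosis rows. It is sound, but it should be stated as an inference.

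**The endpoint is cumulative.** SAP 8.1 introduces the windows for by-visit summaries, while Table 4 counts an event in any window through 6 or 12 months. It is arguable whether the tie-break removes a CT-positive event from a cumulative count. If it does, a persistent kink disappears only if X-ray overrules it in every window. Device deficiencies are also reported on their own form (protocol F.6.3), so a CT-proven kink would not be lost from the study record.

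**A numerical bias.** A reader might want one, but the documents give no X-ray/CT agreement figures. Suppose, purely as an assumption, a 5% CT-defined rate, X-ray positive in 30% of CT positives, and a persistent kink imaged in three windows. The retained rate is 5% × 0.3 = 1.5% if the reads are fully correlated, but 5% × (1 − 0.7³) = 3.3% if they are independent. X-ray false positives would push the other way and could accumulate over windows. No single figure is defensible.

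**Separate reads may not exist.** The effect requires a kink or twist result for each modality. The core lab guidelines are held elsewhere, so the documents do not show whether reads are separate or integrated. Nothing exempts core lab reads from the rule.

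**Conclusion.** The conflict stands. For kinking and twisting, SAP 8.1 with Appendix 12.1 gives the decision to a modality that L.2 does not accept, and following the rule can drop a CT-proven event within a window or count one that CT does not confirm.

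Its reach is small: two items within one descriptive secondary endpoint with no inferential test, and only where modalities disagree within a window. A reader might infer that the primary effectiveness result or the device-failure signal is at risk. The documents do not support that: contrast CT leads every imaging row used in the primary endpoint, and the unanticipated device effects named in protocol J.3 are fractures and detachment. The direction and size of any error in the kinking and twisting rates cannot be determined from the documents.

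The conclusion assumes that results are recorded by modality and that the 8.1 rule is programmed as written.

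**What to change.** Add one sentence to SAP 8.1: the visibility ranking applies only among modalities that the relevant L.2 definition accepts. Kinking and twisting are then scored from CT or angiography. L.2 does not require contrast, so non-contrast CT should stay eligible; protocol Table F-2, footnote a, makes non-contrast CT/MR plus duplex the preferred alternative when contrast is not possible. L.2 does not name MRA either, so the sponsor should state whether it counts as angiography.

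For these two items, define n in Table 4 as subjects with such a readable image in the window, or, in the cumulative rates, a counted event. List X-ray-only appearances of a kink or twist separately.

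Leave the fracture row and all matrix cells as they are, so that SAP 12.1 continues to match protocol L.6.

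The cost is a sentence and a denominator note, with no new imaging or reads. The downside is that subjects with no CT or angiography in the window, such as those followed by duplex plus X-ray only, leave the denominator for these two items. That is consistent with L.2, which cannot be assessed in them.

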## **8.2. Baseline Characteristics and Poolability of Data**

Descriptive data summaries of subject disposition, demographics, baseline characteristics, and subject accountability will be provided.

The poolability of subjects enrolled in the Endurant Evo US Clinical trial and subjects enrolled in the Endurant Evo International Clinical Trial is assumed given that both study protocols will be similar with respect to, inclusion/exclusion criteria, clinical treatment, definitions of clinical events, one data monitoring plan, Data Monitoring Committee (DMC), Clinical Event Committee (CEC), Independent Physician Reviewer (IPR) and core imaging laboratory.

At the data analysis stage, the data poolability will be reviewed for the primary endpoints. Results from Endurant Evo US Clinical Trial and Endurant Evo International Clinical Trial subjects will be presented separately for clinical review as well as tested using a Chi-square test.

A poolability analysis among geographies/investigational sites will be assessed descriptively for the primary endpoints by geographic regions. Small investigational sites (less than 5 subjects) will be grouped with other nearby sites for the by-region analysis.

### **8.3. Handling of Missing Data**

During statistical analysis, imputation of missing data will not be performed except for data related to the onset date of an adverse event or a death. In cases where the onset date of an event or a death is incomplete and unresolvable via data query, the 15th day of the known month or July 1st of the known year will be used.

Sensitivity analysis using tipping point method may be performed, as needed, to assess the impact of missing data.

### **8.4. Analysis of the Primary Endpoints**

#### *Statistical Hypothesis:*

The primary safety endpoint will be tested against a predetermined safety Performance Goal (PG) using the following statistical hypotheses:

$$H_0: p \geq 20\% \text{ vs. } H_1: p < 20\%$$

where  $p$  is the proportion of subjects experiencing a MAE within 30 days of the index procedure in the target population of subjects treated with the Endurant Evo AAA Stent graft system and 20% is the safety PG.

The primary effectiveness endpoint will be tested against a predetermined effectiveness PG using following statistical hypotheses:

$$H_0: q \leq 80\% \text{ vs. } H_1: q > 80\%$$

where  $q$  is the proportion of subjects who have a successful aneurysm treatment in the target population of subjects treated with the Endurant Evo AAA Stent graft system and 80% is the effectiveness PG.

If the null hypothesis ( $H_0$ ) is rejected at the one-sided 0.025 statistical significance level, it is considered that the PG for the associated endpoint has been reached.

Both safety and effectiveness endpoints are dichotomous study outcomes; hence, an exact method based on the binomial distribution will be used for the hypothesis testing.

#### *MAE Rate Calculation:*

All MAEs will be adjudicated by the Clinical Event Committee (CEC) per protocol. MAE rate will be calculated as follows (Table 3):

**Table 4: Imaging based Event Rate Calculation:**

Event rate = $m/n$	At 1 Month	At 6 Months	At 12 Months
$m = \text{No. of Subjects Who Had Event(s)}$	No. of subjects who had an event with scan day within the 1-month window.	No. of subjects who had an event with scan day within the 6-month window.	No. of subjects who had an event with scan day within the 12-month window.
$n = \text{No. of Subjects Who Had Readable Images}$	No. of subjects who had a readable image within the 1-month window.	No. of subjects who had a readable image within the 6-month window.	No. of subjects who had a readable image within the 12-month window.
Event rate = $m/n$	Through 1 Month	Through 6 Months	Through 12 Months
$m = \text{No. of Subjects Who Had Event(s)}$	No. of subjects who had an event with scan day within the 1-month window.	No. of subjects who had an event with scan day within 1- or 6-month windows.	No. of subjects who had an event with scan day within 1-, 6- or 12-month windows.
$n = \text{No. of Subjects Who Had Readable Images}$	No. of subjects who had a readable image within the 1-month window.	No. of subjects who had an event (counted in m) or had a readable image within the 6-month window.	No. of subjects who had an event (counted in m) or had a readable image within the 12-month window.

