Stent Graft Migration	
Stent graft migration can be attributed to migration of the main body stent graft or migration of a stent graft limb/extension.
 
Main body stent graft migration is defined as evidence of movement of the main body stent graft relative to fixed anatomic landmarks, which is not due to remodeling of the subject's vasculature. Proximal migration is observed when the stent graft completely covers a renal artery or movement is > 10 mm. Distal migration is observed when the stent graft moves > 10 mm distally relative to fixed anatomic landmarks.
 
Stent graft limb/extension migration is defined as evidence of movement of the stent graft limbs/extensions relative to fixed anatomic landmarks, which is not due to remodeling of the subject's vasculature. Proximal migration is observed when the distal part of the stent graft limb/extension moves > 10 mm proximally. Distal migration is observed when the distal part of the stent graft limb/extension moves > 10 mm distally or completely covers the internal iliac artery.

Secondary Procedures	A secondary procedure is defined as any endovascular or surgical procedure performed following the completion of the operative initial

Secondary Endpoints:	Definition
	implantation procedure (thus on subsequent occasion after final closure of the last artery access site) which involves the targeted vascular segment treated by the Endurant Evo AAA stent graft system, including access sites and bypasses of the targeted vascular segment in which there is either manipulation of the implanted Endurant Evo stent graft or implantation of any additional devices. (Procedures related to complications due to the use of a closure device are excluded from this definition)
Aneurysm Expansion	Aneurysm maximum diameter increase >5 mm as compared to the 1- month contrast enhanced imaging measurements.
Aneurysm Rupture	Rupture or perforation of the targeted abdominal aneurysmal sac as detected by angiography, CT scan, and/or direct observation at surgery or autopsy. Aneurysm rupture should be reported as either procedure-related aneurysm rupture, (i.e., perforation of the aneurysm during the course of the implantation procedure), or as a late aneurysm rupture that follows device deployment. Excluded are aneurysms in anatomic areas other than the targeted segment treated by the Endurant Evo AAA Stent graft system.

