## 8.5. Analysis of the Secondary Endpoints

Descriptive statistical analyses will be performed on secondary endpoints. No inferential statistical analysis is planned for secondary endpoints.

Event rates such as mortality, secondary procedures, serious adverse events, conversion to open surgery, and aneurysm ruptures will be calculated in the same way as the MAE rate, specified in Table 3.

The survival from all-cause and aneurysm-related mortality over one year time or longer will be presented with the Kaplan-Meier survival curve and the associated Kaplan-Meier estimate will be calculated along with its standard error using the Greenwood method.

Imaging based event rate such as stent graft migration, aneurysm expansion, endoleaks, stent graft occlusions, and device deficiencies will be calculated in the way as specified in Table 4.

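### SAP Table 4 sets no 1-month baseline condition for aneurysm expansion or landmark-based migration, so imaged subjects whose change cannot be measured stay in the denominator and the descriptive rates are understated.

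*SAP*

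**What the plan says.** - **Which endpoints use Table 4.** SAP 8.5: "Imaging based event rate such as stent graft migration, aneurysm expansion, endoleaks, stent graft occlusions, and device deficiencies will be calculated" as Table 4 sets out.
- **Numerator and denominator.** In the 12-month column of SAP Table 4 (section 8.4), m is "No. of subjects who had an event with scan day within the 12-month window" and n is "No. of subjects who had a readable image within the 12-month window". In the 6-month column, n is "No. of subjects who had a readable image within the 6-month window". No cell asks for a 1-month image.
- **Both endpoints are changes from 1 month.** SAP section 5, Secondary Endpoints: "Aneurysm expansion >5 mm at 6- and 12-month follow-up visits (as compared to 1-month imaging") and "Stent graft migration at 6- and 12-month follow-up visits (as compared to 1-month imaging").
- **The baseline is described in two ways.** Protocol L.2 defines expansion "as compared to the 1- month contrast enhanced imaging measurements". The endpoint lists refer only to 1-month imaging and do not mention contrast.
- **The primary endpoint has a similar component.** SAP section 5, Primary Effectiveness Endpoint, includes a greater than 5 mm "increase in maximum diameter as measured on CT scan (or MRA/MRI) at 12-month follow-up as compared to 1-month imaging".
- **Missing data.** SAP 8.3 rules out imputation except for incomplete onset dates of adverse events or death, and makes a tipping-point analysis optional.

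**The concern.** A rate of change needs two measurements per subject, and Table 4 checks for only one. A subject with a good 12-month scan and no usable 1-month measurement has an unknown change. That subject cannot be counted as an expansion event but is still counted in n. In effect, an unknown result is reported as no expansion, and the error always favours the device.

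Table 4 is a single template for several findings. It suits endoleak and occlusion, which can be read from the visit image alone. It does not suit a finding defined against an earlier image.

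At stake are the 6- and 12-month expansion rates and the part of the migration rate that depends on measured movement. A related gap is that the SAP does not say how the tested effectiveness composite classifies a subject whose diameter change cannot be assessed.

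**Working it through.** **1. Reference sample size.** SAP 3.3 gives 119 evaluable subjects at 12 months, from 140 enrolled with 15% attrition: 119 / 0.85 = 140, which reproduces. With an exact binomial test of 80% against 90.5% at one-sided 0.025, n = 119 needs at least 104 successes (attained level 0.0241) and has 90.1% power, matching the stated 90%. I use 119 below as an illustrative number of subjects imaged at 12 months.

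**2. Bias formula.** Let N subjects have a readable 12-month image, let a share u of them have no usable 1-month measurement, and let p be the expansion rate among those with both. Assume a missing baseline is unrelated to outcome.

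- Events that can be detected: p × (1 − u) × N
- Table 4 denominator: N
- Table 4 rate: p × (1 − u)

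The relative understatement is u and the absolute understatement is p × u. The 6-month column behaves in the same way.

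**3. Size.** The documents do not give u, so 2% to 15% is an assumption.

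| True rate p | u = 2% | u = 5% | u = 10% | u = 15% |
|---|---|---|---|---|
| 5% | 4.90% | 4.75% | 4.50% | 4.25% |
| 10% | 9.80% | 9.50% | 9.00% | 8.50% |

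**4. The same in counts, with 119 imaged at 12 months.**

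| Events | Table 4 rate | 3 without baseline (n = 116) | 6 (n = 113) | 12 (n = 107) | 18 (n = 101) |
|---|---|---|---|---|---|
| 5 | 4.20% | 4.31% | 4.42% | 4.67% | 4.95% |
| 10 | 8.40% | 8.62% | 8.85% | 9.35% | 9.90% |

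For scale, the standard error of a 5% rate at n = 119 is √(0.05 × 0.95 / 119) = 2.0 percentage points. The bias at a true 5% is 0.1 to 0.75 points.

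**5. What bears on u.** Two provisions keep it low: the 1-month analysis window is Days 1 to 90 (SAP Table 2), and a CT/MR taken at discharge or before Day 15 can serve as the 1-month scan (Protocol F.2.3). One could raise it: Protocol Table F-2, footnote a, allows duplex plus X-ray when CT/MR is not possible. SAP Appendix 12.1 rates duplex 3 and X-ray 4 for aneurysm diameter, and X-ray 3 and duplex 4 for migration, where 3 is not very visible and 4 is invisible.

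**6. Why the composite rule should be written down.** Take the boundary result of 104/119, which passes against 80% (one-sided exact p = 0.024). If 3 of those 104 had no assessable diameter change and were treated as missing, the result would be 101/116, p = 0.032, which does not pass. With 6 it would be 98/113, p = 0.043. This is a chosen boundary case. It shows only that the classification can decide the test; the SAP prescribes neither classification.

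**The case against.** **Readable may mean readable for the finding in question.** Table 4 covers several findings, and Appendix 12.1 rates endoleak as invisible on non-contrast CT, so the word makes most sense finding by finding. That is fair, but it does not close the gap. Table 4 attaches the word to the image in the visit window, and a 12-month scan can be fully readable for diameter when no 1-month diameter exists. The bar on imputation in SAP 8.3 does not help either, because it removes nobody from n.

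**The effect is small and u is assumed.** This stands. The wide 1-month window should leave few subjects without a baseline, the bias is well inside sampling error, and SAP 8.5 plans no inference on these rates.

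**Stronger readings that the documents do not support:**

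- *Table 4 makes unassessable subjects successes in the primary composite.* A reader might infer this because the table sits in the primary-endpoint section. But the table gives rates for single imaging events, SAP 8.5 sends the secondary imaging rates to it, and the only rule tied to the primary endpoint there is that its imaging components use core lab reads. No composite denominator is given. That is an omission and not a prescribed error.
- *A non-contrast 1-month scan can never serve as baseline.* Only L.2 requires contrast. The endpoint lists do not, and Appendix 12.1 rates diameter on non-contrast CT and MRI as visible. The two wordings conflict, and neither can be assumed to govern.
- *Migration can never be an event without a 1-month image.* L.2 also counts complete coverage of a renal artery (main body) or of the internal iliac artery (limb or extension), which might be seen on a later scan alone. Only the part based on distance moved is affected.

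**Conclusion.** The concern holds for the descriptive 6- and 12-month expansion rates and for the landmark-movement part of migration. As written, Table 4 estimates p × (1 − u) and not p, so it is biased down whenever u and p are above zero. For an assumed u of 2% to 15%, a true 5% rate is reported as 4.9% to 4.25%. The direction follows from the text. The size rests on two assumptions: the value of u, which the documents do not give and which is probably towards the low end, and missing baselines being unrelated to outcome. For migration as a whole the understatement is smaller than u wherever coverage events are detected without a baseline.

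For the primary effectiveness endpoint the finding is limited to silence: the SAP does not say how a subject with an unassessable diameter change is classified. It should, because the choice can matter near the success boundary.

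**What to change.** 1. **Table 4.** For endpoints defined as change from 1 month, define n at 6 and 12 months as subjects counted in m, or with both a 1-month image and a visit-window image readable for that measurement. Keeping subjects counted in m means that migration shown by complete renal or internal iliac coverage still counts. It also matches the form that Table 4 already uses in its cumulative 6- and 12-month denominators. Report the number excluded for lack of a baseline.
2. **Primary effectiveness composite.** State that a subject whose diameter change cannot be assessed is a failure if any other component failed. Otherwise the subject is missing for the composite and enters the tipping-point analysis, and is not counted as free of growth.
3. **Baseline definition.** Reconcile the contrast requirement in Protocol L.2 with the 1-month imaging wording in the primary and secondary endpoint lists, so that it is clear which 1-month images qualify.

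The cost is a few sentences in the SAP, one alignment with the protocol definition and one programming condition. No new data are needed. The denominators become slightly smaller, and the corrected rate still describes only subjects with both measurements, which is why the excluded count should be shown beside it.
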